5.3.2 Eliciting Adverse Event Information

A consistent methodology of non-directive questioning should be adopted for eliciting adverse event information at all patient evaluation timepoints. Examples of non-directive questions include the following:

"How have you felt since your last clinic visit?"

"Have you had any new or changed health problems since you were last here?"

5.3.3 Assessment of Severity of Adverse Events

The adverse event severity grading scale for the NCI CTCAE (v4.0) will be used for assessing adverse event severity. [Table 6](#) will be used for assessing severity for adverse events that are not specifically listed in the NCI CTCAE.

Table 6 Adverse Event Severity Grading Scale for Events Not Specifically Listed in NCI CTCAE

Grade	Severity
1	Mild; asymptomatic or mild symptoms; clinical or diagnostic observations only; or intervention not indicated
2	Moderate; minimal, local, or non-invasive intervention indicated; or limiting age-appropriate instrumental activities of daily living ^a
3	Severe or medically significant, but not immediately life-threatening; hospitalization or prolongation of hospitalization indicated; disabling; or limiting self-care activities of daily living ^{b, c}
4	Life-threatening consequences or urgent intervention indicated ^d
5	Death related to adverse event ^d

NCI CTCAE = National Cancer Institute Common Terminology Criteria for Adverse Events.

Note: Based on the most recent version of NCI CTCAE (v4.0), which can be found at:
http://ctep.cancer.gov/protocolDevelopment/electronic_applications/ctc.htm

^a Instrumental activities of daily living refer to preparing meals, shopping for groceries or clothes, using the telephone, managing money, etc.

^b Examples of self-care activities of daily living include bathing, dressing and undressing, feeding oneself, using the toilet, and taking medications, as performed by patients who are not bedridden.

^c If an event is assessed as a "significant medical event," it must be reported as a serious adverse event (see Section 5.4.2 for reporting instructions), per the definition of serious adverse event in Section 5.2.2.

^d Grade 5 events must be reported as serious adverse events (see Section 5.4.2 for reporting instructions), per the definition of serious adverse event in Section 5.2.2.

5.3.4 Assessment of Causality of Adverse Events

Investigators should use their knowledge of the patient, the circumstances surrounding the event, and an evaluation of any potential alternative causes to determine whether an adverse event is considered to be related to the study drug, indicating "yes" or "no" accordingly. The following guidance should be taken into consideration (see also [Table 7](#)):

- Temporal relationship of event onset to the initiation of study drug
- Course of the event, with special consideration of the effects of dose reduction, discontinuation of study drug, or reintroduction of study drug (as applicable)
- Known association of the event with the study drug or with similar treatments
- Known association of the event with the disease under study
- Presence of risk factors in the patient or use of concomitant medications known to increase the occurrence of the event
- Presence of non-treatment-related factors that are known to be associated with the occurrence of the event

Table 7 Causal Attribution Guidance

Is the adverse event suspected to be caused by the study drug on the basis of facts, evidence, science-based rationales, and clinical judgment?	
YES	There is a plausible temporal relationship between the onset of the adverse event and administration of the study drug, and the adverse event cannot be readily explained by the patient's clinical state, intercurrent illness, or concomitant therapies; and/or the adverse event follows a known pattern of response to the study drug; and/or the adverse event abates or resolves upon discontinuation of the study drug or dose reduction and, if applicable, reappears upon re-challenge.
NO	An adverse event will be considered related, unless it fulfills the criteria specified below. Evidence exists that the adverse event has an etiology other than the study drug (e.g., preexisting medical condition, underlying disease, intercurrent illness, or concomitant medication); and/or the adverse event has no plausible temporal relationship to administration of the study drug (e.g., cancer diagnosed 2 days after first dose of study drug).

For patients receiving combination therapy, causality will be assessed individually for each protocol-mandated therapy.

5.3.5 Procedures for Recording Adverse Events

Investigators should use correct medical terminology/concepts when recording adverse events on the Adverse Event eCRF. Avoid colloquialisms and abbreviations.

Only one adverse event term should be recorded in the event field on the Adverse Event eCRF.

5.3.5.1 Infusion-Related Reactions

Adverse events that occur during or within 24 hours after treatment administration and are judged to be related to study treatment infusion (atezolizumab or docetaxel) should be captured as a diagnosis (e.g., "infusion-related reaction") on the Adverse Event eCRF. If possible, avoid ambiguous terms such as "systemic reaction." *Cases of late-onset CRS should be reported as "cytokine-release syndrome" on the Adverse Event eCRF.* Associated signs and symptoms of an IRR should be recorded on the dedicated Infusion-Related Reaction eCRF.

If a patient experiences both a local and systemic reaction to *a single administration* of study treatment, each reaction should be recorded separately on the Adverse Event eCRF, with *associated* signs and symptoms of an IRR also recorded separately on the dedicated Infusion-Related Reaction eCRF.

5.3.5.2 Diagnosis versus Signs and Symptoms

A diagnosis (if known) should be recorded on the Adverse Event eCRF rather than individual signs and symptoms (e.g., record only liver failure or hepatitis rather than jaundice, asterixis, and elevated transaminases). However, if a constellation of signs and/or symptoms cannot be medically characterized as a single diagnosis or syndrome at the time of reporting, each individual event should be recorded on the Adverse Event eCRF. If a diagnosis is subsequently established, all previously reported adverse events based on signs and symptoms should be nullified and replaced by one adverse event report based on the single diagnosis, with a starting date that corresponds to the starting date of the first symptom of the eventual diagnosis.

5.3.5.3 Adverse Events That Are Secondary to Other Events

In general, adverse events that are secondary to other events (e.g., cascade events or clinical sequelae) should be identified by their primary cause, with the exception of severe or serious secondary events. A medically significant secondary adverse event that is separated in time from the initiating event should be recorded as an independent event on the Adverse Event eCRF. For example:

- If vomiting results in mild dehydration with no additional treatment in a healthy adult, only vomiting should be reported on the eCRF.
- If vomiting results in severe dehydration, both events should be reported separately on the eCRF.
- If a severe gastrointestinal hemorrhage leads to renal failure, both events should be reported separately on the eCRF.
- If dizziness leads to a fall and consequent fracture, all three events should be reported separately on the eCRF.
- If neutropenia is accompanied by an infection, both events should be reported separately on the eCRF.

All adverse events should be recorded separately on the Adverse Event eCRF if it is unclear as to whether the events are associated.

5.3.5.4 Persistent or Recurrent Adverse Events

A persistent adverse event is one that extends continuously, without resolution, between patient evaluation timepoints. Such events should only be recorded once on the Adverse Event eCRF. The initial severity (intensity or grade) of the event will be recorded at the time the event is first reported. If a persistent adverse event becomes more severe, the most extreme severity should also be recorded on the Adverse Event eCRF. If the event becomes serious, it should be reported to the Sponsor immediately (i.e., no more than 24 hours after learning that the event became serious; see Section 5.4.2 for reporting instructions). The Adverse Event eCRF should be updated by changing the event from "non-serious" to "serious," providing the date that the event became serious, and completing all data fields related to serious adverse events.

A recurrent adverse event is one that resolves between patient evaluation timepoints and subsequently recurs. Each recurrence of an adverse event should be recorded as a separate event on the Adverse Event eCRF.

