5.2.1 Adverse Events

According to the ICH guideline for Good Clinical Practice, an adverse event is any untoward medical occurrence in a clinical investigation subject administered a pharmaceutical product, regardless of causal attribution. An adverse event can therefore be any of the following:

- Any unfavorable and unintended sign (including an abnormal laboratory finding), symptom, or disease temporally associated with the use of a medicinal product, whether or not considered related to the medicinal product
- Any new disease or exacerbation of an existing disease (a worsening in the character, frequency, or severity of a known condition), except as described in Section 5.3.5.10
- Recurrence of an intermittent medical condition (e.g., headache) not present at baseline

- Any deterioration in a laboratory value or other clinical test (e.g., ECG, X-ray) that is associated with symptoms or leads to a change in atezolizumab treatment or concomitant treatment or discontinuation from study drug
- Adverse events that are related to a protocol-mandated intervention, including those that occur prior to assignment of atezolizumab treatment (e.g., screening invasive procedures such as biopsies)

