##### Neoadjuvant Atezolizumab Therapy Phase

For the Neoadjuvant Atezolizumab Therapy Phase of the study, an adverse event will be any event that starts following the start of the first dose of study drug for those subjects not continuing in the Surveillance/Survival Follow-up Phase of the study, and through the day immediately preceding the start date of the first adjuvant cycle for subjects continuing in the Surveillance/Survival Follow-up Phase of the study.

---

If the onset date and/or resolution date of an adverse event is incomplete (for example, only the month and year are available), the event will be assumed to start after the first dose of study drug, as long as the available information does not conclusively indicate that the event emerged prior to the start date of the first cycle of study drug administration.

An overview of adverse events will present the number and percentage of safety population subjects who have at least one AE, at least one Grade 3 or higher AE, at least one treatment related AE, at least one serious AE, at least one AE of special interest, at least one AE leading to study drug withdrawal, at least one AE leading to death, and at least one treatment related AE leading to death, overall (subjects counted only once if any AE is experienced) and by highest NCI CTCAE grade (subjects counted only once at the highest grade level experienced).

The number and percentage of safety population subjects with AEs will be summarized by SOC and PT in total, and by highest NCI CTCAE grade. At each summary level, a subject will be counted only once if he/she experiences at least one AE, and when summarizing by highest NCI CTCAE grade, a subject will be counted only once at the highest grade level experienced. AE summary tables will be sorted by descending occurrence rate according to the SOC, and then by descending occurrence rate within PT. The following types of AE summaries will be prepared:

- All AE
- Grade  $\geq 3$  AE
- Onset date prior to date of surgery (Neoadjuvant Atezolizumab Therapy Phase only)
- Onset date on or after date of surgery, for safety population with surgery date (Neoadjuvant Atezolizumab Therapy Phase only)
- Treatment related AE
- Serious AE
- AE of special interest
- AE leading to death
- Treatment related AE leading to death
- AEs leading to study drug withdrawal

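### An unresolved adverse event that worsens or becomes serious after resection is tabulated, at its worst, as a pre-surgery event and is left out of the post-surgery tables

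*Protocol*

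**What the plan says.** Protocol 5.3.5.4 separates persistent from recurrent events. Of a persistent event it says: "Such events should only be recorded once on the Adverse Event eCRF". On grading: "The initial severity (intensity or grade) of the event will be recorded at the time the event is first reported". On worsening: "If a persistent adverse event becomes more severe, the most extreme severity should also be recorded on the Adverse Event eCRF". If the event turns serious, the site amends the same record, "providing the date that the event became serious". No date is requested for a rise in grade. A recurrent event is handled differently: "Each recurrence of an adverse event should be recorded as a separate event on the Adverse Event eCRF".

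SAP 6.4.1, under the neoadjuvant phase, lists among its summaries "Onset date prior to date of surgery (Neoadjuvant Atezolizumab Therapy Phase only"), with a counterpart for onset on or after the surgery date. When events are summarised by grade, "a subject will be counted only once at the highest grade level experienced". SAP Section 7, Table 3 turns this into three pairs of outputs split at surgery: all events (14.3.1.2b/c), treatment-related events (14.3.1.4a/b) and serious events (14.3.1.5b/c). All six are flagged for the safety interim, the efficacy interim and the primary analysis.

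SAP 6.4.1 also defines the two phases. For patients who continue, the neoadjuvant phase stops on the day before the first adjuvant cycle. The Surveillance/Survival Follow-up phase takes any event in continuing patients that begins after the first dose of study drug.

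**The concern.** The recording rule and the tabulation rule do not fit together. The record can carry a grade, or a serious status, that was reached after surgery, but the only date the SAP uses to place it is the onset. Protocol 5.2.1 includes in its definition of an adverse event "Any new disease or exacerbation of an existing disease (a worsening in the character, frequency, or severity of a known condition"), yet 5.3.5.4 opens no new record for such a worsening, and the SAP has no rule for it.

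Protocol 6.7.1.1 says that data on thoracic resection after a checkpoint inhibitor are still limited and gives this as the reason for the safety interim. The tables split at surgery are the planned outputs that bear most directly on that question. The misplacement runs one way: it can raise apparent pre-surgery severity and lower apparent post-surgery severity, never the reverse.

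**Working it through.** The plan states no figure on this point, so there is nothing to reproduce. The check follows hypothetical event histories through the two documents.

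**Timing (Protocol Appendix 1).** The second dose is on Day 22 and surgery on Day 40 (±10), so nominally 40 − 22 = 18 days separate them. A low-grade event still open at surgery is therefore plausible. Section 5.3.1 and Table 5 limit what can follow. Without adjuvant atezolizumab, non-serious events are reported to Day 22 + 30 = Day 52, nominally 52 − 40 = 12 days after surgery. Serious events and events of special interest are reported to Day 22 + 90 = Day 112, nominally 72 days after surgery. With adjuvant atezolizumab, reporting is not interrupted.

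**History 1, grade.** Grade 1 onset on Day 30, surgery on Day 40, the same unresolved event reaches Grade 3 on Day 45.
- Protocol 5.3.5.4: one record, with initial grade 1 and most extreme grade 3. Onset stays at Day 30. That is an inference from the single record. The protocol says it outright only in 5.3.5.2, where a diagnosis replacing earlier symptoms takes the start date of the first symptom.
- SAP 6.4.1: Day 30 precedes Day 40, so the event enters Table 14.3.1.2b as Grade 3 and does not enter 14.3.1.2c. If judged related, it enters 14.3.1.4a and not 14.3.1.4b.

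**History 2, seriousness.** The same event, becoming serious on Day 45. The protocol requires that date, but the SAP still places the event by onset. It enters Table 14.3.1.5b and is absent from 14.3.1.5c.

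**History 3, adjuvant phase.** Grade 1 onset before surgery, unresolved, Grade 3 during adjuvant atezolizumab. Onset precedes the first adjuvant cycle, so it is Grade 3 in the neoadjuvant table (14.3.1.2.1). Onset also follows the first dose of study drug, so under the literal Surveillance/Survival Follow-up definition it is Grade 3 in 14.3.1.2.2 as well. It is counted twice.

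**Is there a correcting rule elsewhere?** The adverse event date rules in SAP 6.1.2 and 6.4.1 deal only with missing or partial dates. Nothing addresses a rise in grade or a change to serious.

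**Would dating only the worst grade be enough?** No. Take an event that is Grade 1, then Grade 2 before surgery, then Grade 3 after it. The record holds grades 1 and 3. A date for Grade 3 moves that grade to the right period, but the Grade 2 reached before surgery cannot be recovered. The date of each increase is needed.

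**The case against.** The strongest reply is that grouping by onset is a recognised choice and the table titles say so. That stands as far as the onset label goes. But the tables also display the highest grade, and a reader will take that grade as belonging to the period shown.

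Second, the affected set is narrow, and this stands. Recurrences get new records. Under 5.3.5.3, so do medically significant secondary events that are separated in time from their cause, and so do events whose association is unclear. A severe postoperative respiratory event may well be entered separately. Under 5.3.5.9 a condition present at screening becomes an adverse event only once it worsens.

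Third, the case report form is not among the documents and may already date grade changes. This also stands, and it makes any request for a new field conditional.

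Fourth, other outputs keep the worst grade in view: the combined table (14.3.1.2a), the Grade 3 or higher and related-death tables (14.3.1.3.1, 14.3.1.9.1), which are not split at surgery, and the event listings. That is correct. They do not, however, show on which side of surgery the worst grade was reached.

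Two stronger readings are tempting. A reader might infer that worsening under adjuvant atezolizumab drops out of the adjuvant tables and that rates there are too low. The Surveillance/Survival Follow-up definition does not support this: it has no cut at the first adjuvant cycle, so the event appears in both phase tables. It would be missing only if the first adjuvant dose was meant, which the text does not say. A reader might also infer that the safety stopping rule is compromised. That rule counts related Grade 5 events without regard to surgery, so the split does not touch it.

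**Conclusion.** The point holds for the split at surgery. An unresolved event that begins before resection and worsens or becomes serious afterwards is shown at its worst before surgery and is absent after it, in the paired tables for all, related and serious events. The direction is fixed: post-surgery severity is understated or unchanged, and pre-surgery severity is overstated or unchanged.

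The size is unknown. The documents give no rate of worsening across surgery, and the symptom rates they report for atezolizumab in lung cancer come from locally advanced or metastatic disease, so no percentage should be attached. The conclusion assumes that the first onset date is kept on the single record.

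In the phase tables the defect is that the neoadjuvant table absorbs later worsening while the literal follow-up definition counts the same event again. The two definitions need to be reconciled. Overall this is a modest fault in tables that serve a stated safety question, and part of it can be repaired from data already required.

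**What to change.** 1. In SAP 6.4.1, place an event in the pre- or post-surgery serious-event table (14.3.1.5b/c) by the date it became serious. Sites must already supply that date, so this is a text and programming change only.
2. For the grade tables split at surgery, count an event whose grade rose after surgery in the post-surgery table at the new grade, and in the pre-surgery table only at the grade reached before surgery. Use the date of each grade increase, and add it to the adverse event form if it is not already there. Where these dates are unavailable, footnote the tables to say that the highest grade may have been reached after surgery.
3. Reconcile the neoadjuvant and Surveillance/Survival Follow-up definitions in SAP 6.4.1 so that one phase rule applies.

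The cost is a short SAP passage, some programming, adjusted table titles and possibly additional date collection on the form. One persistent event can then appear in both periods, which a footnote should explain. Grade-change dates may be incomplete for patients already treated, and for them the footnote in step 2 is the fallback.

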5.3.5.5 Abnormal Laboratory Values

Not every laboratory abnormality qualifies as an adverse event. A laboratory test result must be reported as an adverse event if it is a change from baseline and meets any of the following criteria:

- Is accompanied by clinical symptoms
- Results in a change in atezolizumab treatment (e.g., dosage modification, treatment interruption, or treatment discontinuation)
- Results in a medical intervention (e.g., potassium supplementation for hypokalemia) or a change in concomitant therapy
- Is clinically significant in the investigator's judgment

Note: For oncology trials, certain abnormal values may not qualify as adverse events.

It is the investigator's responsibility to review all laboratory findings. Medical and scientific judgment should be exercised in deciding whether an isolated laboratory abnormality should be classified as an adverse event.

If a clinically significant laboratory abnormality is a sign of a disease or syndrome (e.g., ALP and bilirubin $5 \times$ ULN associated with cholestasis), only the diagnosis (i.e., cholestasis) should be recorded on the Adverse Event eCRF.

If a clinically significant laboratory abnormality is not a sign of a disease or syndrome, the abnormality itself should be recorded on the Adverse Event eCRF, along with a descriptor indicating whether the test result is above or below the normal range

(e.g., "elevated potassium," as opposed to "abnormal potassium"). If the laboratory abnormality can be characterized by a precise clinical term per standard definitions, the clinical term should be recorded as the adverse event. For example, an elevated serum potassium level of 7.0 mEq/L should be recorded as "hyperkalemia."

Observations of the same clinically significant laboratory abnormality from visit to visit should only be recorded once on the Adverse Event eCRF (see Section [5.3.5.4](#) for details on recording persistent adverse events).

5.3.5.6 Abnormal Vital Sign Values

Not every vital sign abnormality qualifies as an adverse event. A vital sign result must be reported as an adverse event if it is a change from baseline and meets any of the following criteria:

- Is accompanied by clinical symptoms
- Results in a change in atezolizumab treatment (e.g., dosage modification, treatment interruption, or treatment discontinuation)
- Results in a medical intervention or a change in concomitant therapy
- Is clinically significant in the investigator's judgment

It is the investigator's responsibility to review all vital sign findings. Medical and scientific judgment should be exercised in deciding whether an isolated vital sign abnormality should be classified as an adverse event.

If a clinically significant vital sign abnormality is a sign of a disease or syndrome (e.g., high blood pressure), only the diagnosis (e.g., hypertension) should be recorded on the Adverse Event eCRF.

Observations of the same clinically significant vital sign abnormality from visit to visit should only be recorded once on the Adverse Event eCRF (see Section [5.3.5.4](#) for details on recording persistent adverse events).

